10. STATISTICAL ANALYSES

10.1. Randomization, Stratification, and Masking

Eligible subjects will be randomly assigned to each of treatment groups in a balanced ratio according to a validated SAS® computer-generated central randomization schedule. The randomization schedule contains the coded treatment assignments for each randomization number. The randomization plan will be based on the study design, number of treatment groups and number of sites.

The randomization schedule is generated by an un-masked statistician who is not affiliated with the study. The randomization schedule is shared with the Sponsor's designee responsible for final clinical packaging and labeling to allow for proper packaging and labeling of the study drug supply. Access to the randomization code will be strictly controlled according to the Sponsor designee's Standard Operating Procedures (SOPs).

The randomization is not unmasked until the study is complete and the database is locked. The Sponsor will confirm in writing that there are no regulatory or quality issues which preclude the unmasking of the study.

Unmasking of the randomization code prior to study completion due to a medical emergency will be managed in accordance with the Sponsor designee's SOP. All unmasked cases will be fully documented. Otherwise, the study mask will remain intact.

In this double-masked study, the investigator and his/her study staff, the subject (including caregiver, if applicable) and Sponsor/designee (other than as stated above) are masked to the identity of the study drug.

10.2. Efficacy and Safety Variables

Primary Efficacy Endpoint(s): The primary endpoint is a reduction of $\geq 10\%$ in patient-reported DED symptoms and impact of symptoms on daily life at Day 84 as defined by the UNC DEMS with SURF-100 as compared to 5% lifitegrast ophthalmic solution, 0.05% cyclosporine ophthalmic emulsion, and vehicle. Subjects not responding to study treatment (non-responders) and who receive another therapeutic treatment for the signs and symptoms of dry eye at or prior to Visit 6 (Day 84) will be treated as failures.

Secondary Efficacy Endpoints:

- Tear Break-up Time: Average increase in TBUT at Day 84 for SURF-100 compared to 5% lifitegrast ophthalmic solution, 0.05% cyclosporine ophthalmic emulsion, and vehicle.
- Schirmer tear test: Average increase in Schirmer tear test score (with anesthesia) at Day 84 for SURF-100 compared to 5% lifitegrast ophthalmic solution, 0.05% cyclosporine ophthalmic emulsion, and vehicle.

Safety Variables: AEs (including SAEs), BCVA, IOP, conjunctival hyperemia, biomicroscopic and ophthalmoscopic findings.

10.3. Analysis Populations

Safety Population: The safety population includes all randomized subjects who receive at least 1 dose of the study drug. Subjects in the safety population will be analyzed in the treatment group for the study drug they received.

Intent-to-Treat Population: The Intent-to-Treat (ITT) population includes all randomized subjects. Subjects in the ITT population will be analyzed in the treatment group to which they were assigned by the randomization schedule, regardless of which study drug they receive.

Per Protocol Population: The per-protocol (PP) population includes all subjects in the ITT population who have no significant protocol deviations during the study.

10.4. Data Handling: Handling of Missing Data

All missing data will generally not be imputed unless otherwise specified. For subjects who are withdrawn from the study prior to study completion, all data compiled up to the point of discontinuation will be used for analysis. All study discontinuations will be included in all analyses up to the time of study discontinuation. As per the protocol, an ITT analysis with the last-observation-carried-forward (LOCF) method will be conducted for the primary efficacy analysis.

For the classification of treatment emergent adverse events (TEAEs) and concomitant medications, the following will be applied in case of missing/incomplete dates:

- If all dates/times (start and stop) are missing, the event/medication will automatically be classified as a TEAE/concomitant medication.
- For AE/medication with a missing start date/time, if the event end date/time is prior to first study drug administration, the event will not be classified as a TEAE/concomitant medication.
- If only the AE start year/medication end year is present and is the same or is after the first study drug administration year unit, the event/medication will be classified as a TEAE/concomitant medication.
- If the AE start month and year/medication end month and year are present and are the same or after the first study drug administration month and year units, the event/medication will be classified as a TEAE/concomitant medication.

10.5. Statistical Methods: General Considerations

All final statistical analyses will be performed after the study database has been locked, unmasked, and released for statistical analysis. All tables, statistical analyses, figures, and subject data listings will be generated using SAS® Version 9.4 or later (SAS Institute Inc., Cary, North Carolina, United States of America).

All data in the database will be presented in the data listings. Unless otherwise stated, all listings will be sorted by treatment group, subject number and assessment visit, as appropriate.

Unless otherwise stated, continuous variables will be summarized using descriptive statistics including number of non-missing observations (n), mean, standard deviation (SD), median, minimum and maximum values. The minimum and maximum values will be presented to the same number of decimal places as the eCRF or laboratory reported data; mean, SD, and median will be presented to one more decimal place than the source data.

Categorical variables will be summarized with frequency counts and percentages. The population size (N for sample size and n for available data) and the percentage (of available data) for each class of the variable will be presented. Percentages will be rounded to one decimal place, with the denominator being the number of patients in the relevant population, unless otherwise stated.

Only data from nominal protocol scheduled visits will be included in the summary tables. Data

from unscheduled visits will not be included in the summary tables but will be included in the figures and listings.

It should be noted that in this study the analysis unit is subject. When data from both eyes are available, data will not be pooled together for the analysis because eyes from the same subject are not independent samples. Statistical analysis generally requires independent samples. Each subject has a designated study eye as per the protocol. Therefore, separate analysis will be conducted for study eye and fellow eye as appropriate.

All confidence intervals (CIs) of the parameter estimates will be two-sided and at the significance level of 0.05 unless otherwise stated.

All data summaries and data listings will use the nominal visit names as captured in the eCRF and as per the protocol schedule of visits. Derived visit windows will not be used for the data analysis. For all ‘by visit’ summary analyses of efficacy and safety endpoints, if a subject has an early discontinuation before Visit 6/Day 84, the data from the early discontinuation visit will be included in Visit 6/Day 84 assessment. If a subject has an early discontinuation after Visit 6/Day 84 but before Visit 7/Day 98, the data from the early discontinuation visit will be included in Visit 7/Day 98 assessment.

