Average increase in TBUT at Day 84 for SURF-100 compared to vehicle, 0.05% cyclosporine ophthalmic emulsion, and 5% lifitegrast ophthalmic solution.

2. Schirmer Tear Test

Average increase in Schirmer score test (with anesthesia) at Day 84 for SURF-100 compared to vehicle, 0.05% cyclosporine ophthalmic emulsion, and 5% lifitegrast ophthalmic solution.

Biomicroscopy and ophthalmoscopy study examinations should be performed by the same board-certified ophthalmologist or a board-certified or state licensed optometrist (that would allow them legally to diagnose and treat patients independently) from visit to visit. All other ratings and procedures should be performed by the same examiner from visit to visit whenever possible.

Additional exams may be scheduled as necessary to ensure the safety of the subjects during the study period.

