| Betamethasone sodium phosphate (BSP) | 
Ocular adverse reactions which may occur with SURF-100 based on marketed ophthalmic corticosteroids include the following:
 
 • Prolonged intensive use of corticosteroids may result in IOP increase, glaucoma with damage to the optic nerve, posterior subcapsular cataracts, thinning of the globe and eventual perforation, secondary ocular infection, reduced visual acuity and visual field defects, mydriasis, ptosis, epithelial punctate keratitis, and corneal calcification may occur. • Delayed healing - The use of steroids after cataract surgery may delay healing and increase the incidence of bleb formation. In those diseases causing thinning of the cornea or sclera, perforations have been known to occur with the use of topical steroids. • Bacterial infections - Prolonged use of corticosteroids may suppress the host response and thus increase the hazard of secondary ocular infections. In acute purulent conditions, steroids may mask infection or enhance existing infection. • Viral infections - Use of ocular steroids may prolong the course and may exacerbate the severity of many viral infections of the eye (including herpes simplex). • Fungal infections - Fungal infections of the cornea are particularly prone to develop coincidentally with long-term local steroid application. Fungus invasion must be considered in any persistent corneal ulceration where a steroid has been used or is in use. Fungal culture should be taken when appropriate. |
| Mycophenolic acid (MPA) | Systemic exposure associated with ophthalmic application of MPA has not been evaluated in humans. Adverse reactions from topical ophthalmic administration of MPA have not been established or investigated to date. |
| Cyclosporine ophthalmic emulsion 0.05% | 
To avoid the potential for eye injury and contamination, be careful not to touch the vial tip to your eye or other surfaces.
 
Cyclosporine ophthalmic emulsion 0.05% should not be administered while wearing contact lenses. (Refer to the Cyclosporine Ophthalmic Emulsion 0.05% Prescribing Information).
 |
| Lifitegrast ophthalmic solution 5% | No warnings/precautions are listed in the Lifitegrast Ophthalmic Solution Prescribing Information. (Refer to the Lifitegrast Ophthalmic Solution 5% Prescribing Information). |

Special Warnings and Precautions for Use:

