BCVA: A worsening of 3 lines or more in log of the minimum angle of resolution (logMAR) score in the study eye from baseline or any prior visit should be captured in the source documents and on the appropriate eCRF as an AE.

IOP: An increase from baseline or any prior study visit of 10 mmHg in IOP in the study eye should be captured in the source documents and on the appropriate eCRF as an AE. An IOP of 30 mmHg or higher will be reported as an SAE.

Biomicroscopy: Slit lamp biomicroscopy will be performed to observe the overall health of the eye, including the lid/lashes, conjunctiva, cornea, anterior chamber, iris, and lens. Any biomicroscopy observations noted prior to Screening (Visit 1) should be recorded as ocular medical history. Any treatment-emergent findings (i.e., findings that were not present prior to treatment or a worsening relative to the pretreatment baseline) should be recorded as an AE.

Ophthalmoscopy: A new finding or a significant worsening (2 units or more) from baseline should be recorded as an AE.

AE Considerations: Additional exams may be scheduled as necessary to ensure the safety of the subjects during the study period. Subjects discontinued due to an AE should be seen for post-study follow-up visits, as needed. Adverse events considered related to study drug that have not resolved or stabilized by the final study visit will be followed during post-study follow-up visits at the discretion of the investigator until the incident has resolved or stabilized and will be documented in the source documents and AE eCRF. Where appropriate, additional written reports and documentation will be provided. Adverse events considered not related to study drug that have not resolved or stabilized by the final study visit will be noted as ongoing in the eCRF, followed at the discretion of the investigator, and recorded in the source documents.

Pregnancy: Although pregnancy is not considered an AE, any complication related to pregnancy would be considered an AE and recorded in the source documents and, if applicable, on the AE eCRF. If an SAE is associated with the pregnancy, the SAE should be reported on the SAE Report Form.

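### IOP and BCVA values from unscheduled exams stay out of the summary tables, and the adverse event rules only partly make up for this, chiefly in the study eye

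*Combined protocol and SAP*

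**What the plan says.** Section 10.5 (General Considerations) sets the tabulation rule: "Only data from nominal protocol scheduled visits will be included in the summary tables". It adds that data "from unscheduled visits will not be included in the summary tables but will be included in the figures and listings". Several neighbouring rules in 10.5 allow for exceptions stated elsewhere; this one does not. The same section says "All data in the database will be presented in the data listings".

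Section 2 (Study Design) provides for off-schedule exams, and section 9 repeats the provision: "Additional exams may be scheduled as necessary to ensure the safety of the subjects during the study period".

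Section 9 (Adverse Events) turns certain measurements into events:

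- IOP, AE: "An increase from baseline or any prior study visit of 10 mmHg in IOP in the study eye should be captured".
- IOP, SAE: "An IOP of 30 mmHg or higher will be reported as an SAE". No eye is named.
- BCVA, AE: "A worsening of 3 lines or more in log of the minimum angle of resolution (logMAR) score in the study eye from baseline" or from any earlier visit.

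On corticosteroids, section 6 warns: "Prolonged intensive use of corticosteroids may result in IOP increase, glaucoma with damage to the optic nerve".

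**The concern.** Extra exams are arranged for safety reasons, so their values are more likely to be abnormal than those from routine visits. Under 10.5 they cannot enter any mean, maximum or by-arm count of IOP or BCVA.

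This matters because ocular safety is the first-named objective in section 1, and section 10.2 lists IOP and BCVA as safety variables in their own right, alongside AEs. Two arms (SURF-100 and 0.01% BSP) contain betamethasone, for which the protocol itself anticipates IOP increase. Three arms contain MPA, and section 6 says that adverse reactions to it by the topical ocular route have not been studied. A change that appears and resolves between scheduled visits could leave no trace in the IOP or BCVA tables of any arm.

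**Working it through.** The plan gives no figure to reproduce. The check is to follow a post-dose value from an unscheduled exam through the other rules and see which table, if any, it reaches.

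**1. Measurement tables.** Section 10.5 summarizes continuous variables by n, mean, SD, median, minimum and maximum. With unscheduled visits excluded, the value enters none of these. One class of off-schedule exam is kept: 10.5 places an early-discontinuation visit in the Day 84 or Day 98 summary.

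**2. AE tables.** Section 9 requires AEs to be recorded when they arise from any procedure in the reporting period, whether or not the visit was scheduled. Section 12.1 tabulates TEAEs by SOC and PT, with a separate table for serious TEAEs, and summarizes study-eye and fellow-eye events separately. The numeric triggers in section 9 then give:

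| Finding at an unscheduled exam | Study eye | Treated fellow eye |
|---|---|---|
| IOP of 30 mmHg or higher | SAE, tabulated | SAE as worded, tabulated |
| IOP rise of 10 mmHg or more, staying below 30 mmHg | AE, tabulated | No numeric trigger |
| IOP rise below 10 mmHg, staying below 30 mmHg | No numeric trigger | No numeric trigger |
| BCVA loss of 3 or more lines | AE, tabulated | No numeric trigger |
| BCVA loss of fewer than 3 lines | No numeric trigger | No numeric trigger |
| Size of the change | Figures and listings only | Figures and listings only |

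Where there is no numeric trigger, the finding reaches an AE table only if the investigator judges it an AE under the general definition.

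**3. Fellow eyes.** Section 2 allows the fellow eye to be dosed and says it is then analysed for safety. Section 8 schedules IOP and BCVA in treated eyes at Visits 3 to 7. Fellow-eye values are therefore collected and meant to be analysed, but the 10 mmHg and 3-line triggers do not apply to them.

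**4. Baseline.** Section 10.6 lets unscheduled pre-dose values set the baseline, while 10.5 bars unscheduled post-dose values from the change-from-baseline summaries. The plan thus uses such measurements on one side of the change score only.

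**5. Scale.** With balanced allocation, 280/7 = 40 and 350/7 = 50 subjects per arm, so 2 × 40 = 80 to 2 × 50 = 100 in the two steroid-containing arms. One subject is 1/50 = 2.0% to 1/40 = 2.5% of an arm. Scheduled checks during dosing fall on Days 7, 30 and 60, followed by Day 84, so the gaps after Day 7 are 30 − 7 = 23, 60 − 30 = 30 and 84 − 60 = 24 days. The documents give no rate of unscheduled exams or of IOP or BCVA changes, and no number of treated fellow eyes. The number of values left out of the tables therefore cannot be derived.

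**The case against.** The strongest reply is that the clinically larger changes are already covered. A reader might infer from 10.5 that pressure and vision peaks found at extra exams vanish from the safety results, so that an IOP table could show none where several occurred. The documents do not support that. A study-eye rise of 10 mmHg or a loss of 3 or more lines is a mandatory AE whichever visit reveals it, an IOP of 30 mmHg or higher is an SAE, both are tabulated by arm, and every value is listed.

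Nor do treated fellow eyes go unreported: the 30 mmHg rule names no eye, their scheduled values are measured, 10.5 provides for separate fellow-eye analysis, and 12.1 includes all reported fellow-eye AEs. The rule is also the same in all seven arms, so it is not specific to the steroid arms. The 23 to 30 day gaps come from the visit schedule and not from the tabulation rule; they only show how long an off-schedule value may go without a scheduled one nearby.

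All of this stands, and it narrows the point. It does not close the gaps in the table above: AE tables count subjects and events and do not show mmHg or lines, and listings give no rate by arm.

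A second reply is that a later safety section may already provide a worst-value table. The text available for this review ends within the list of TEAE summaries in 12.1, so this cannot be excluded, and the absence of such a table here is not evidence that the plan lacks one. As worded, though, the 10.5 rule would govern that table too unless it says otherwise.

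**Conclusion.** The point holds in a limited form. Section 10.5 keeps unscheduled IOP and BCVA values out of the measurement summaries in every arm, and the AE rules recover only part of them. What the tables can miss is:

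- in treated fellow eyes, an IOP rise of 10 mmHg or more that stays below 30 mmHg, or a loss of 3 or more lines, unless the investigator reports it as an AE;
- in study eyes, changes below the AE thresholds, with the same proviso;
- in either eye, the size of a peak.

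The number of subjects affected is unknown, and no percentage should be attached to it. The conclusion assumes that the 10.5 rule is applied as written and that no later section overrides it. It concerns safety reporting only and does not touch the efficacy analyses. The change is inexpensive and should be made.

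**What to change.** Keep the by-visit summaries on nominal visits. State in sections 10.5 and 12, as an exception to the rule, that worst post-baseline IOP and BCVA will be summarized by arm from scheduled and unscheduled values together, separately for study eyes and treated fellow eyes. Include counts at the protocol's own thresholds: IOP rise of 10 mmHg or more, IOP of 30 mmHg or higher, and loss of 3 or more lines. Use the number of treated fellow eyes in each arm as the fellow-eye denominator, since section 2 makes fellow-eye dosing optional and 12.1 itself calls these eyes a selective sample.

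If a later safety section already contains such a table, it is enough to state there that unscheduled visits are included.

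The cost is about one sentence in the SAP and two tables. The drawback is that subjects examined more often have more chances to show a peak, which a footnote should say. No visit, dosing or AE reporting rule changes.

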10.6. General Derived and Transformed Data

Age, in completed years, at informed consent date will be defined as: Age (years) = integer value (Date of Informed Consent – Date of Birth + 1) / 365.25).

Study day will be calculated using the first dosing date as the reference date. If the date of interest occurs on or after the first dosing date, then study day will be calculated as (date of interest – date of first dosing) + 1. If the date of interest occurs prior to the first dosing date, then study day will be calculated as (date of interest – date of first dosing). The day of the first dosing will be identified as Study Day 1 according to Clinical Data Interchange Standards Consortium (CDISC) standard. In the protocol, the first dosing day is denoted as Day 0, which is corresponding to Study Day 1. Data listings will present study days in addition to assessment dates, where applicable. As per above, all data summaries and data listings will use the nominal visit names as captured in the eCRF and as per the protocol schedule of visits. The calculated study day as per CDISC will only be used in data listings to indicate the distance of an event from the dosing day.

Baseline will be defined as the last available, non-missing observation prior to the first dosing time with study drug, unless specifically mentioned otherwise. When baseline is derived, all data before the first dosing with study drug, including unscheduled visits before the first dosing with study drug, will be used for the derivation of baseline value.

Change from Baseline: Assessment value at post-dosing visit – baseline value. It should be noted that if the derived baseline as above is missing for one parameter, then the change from baseline will not be available for this parameter. Imputation of baseline data will not be conducted.

Percentage Change from Baseline:

(Assessment value at post-dosing visit – baseline value)*100 / baseline value

11. EFFICACY

11.1. Primary Efficacy Analysis

Subjects with a 10% or more reduction in UNC DEMS score from baseline are defined as responders, and response rates at Visit 6 (Day 84) will be summarized by treatment group. All other subjects with non-missing data will be treated as non-responders. Further, subjects who received non-study therapeutic treatment for the signs and symptoms of dry eye at or prior to Visit 6 (Day 84) will be treated as non-responders (treatment failure) from the time of receiving non-study therapeutic treatment regardless of whether the UNC DEMS score is available at the relevant visit. For the ITT analysis, subjects with a missing UNC DEMS score at a visit will be imputed by the LOCF method. Therefore, there will be no missing data for ITT analysis. The response rate will be summarized at Visit 6 (Day 84) by treatment group, along with its 95% CI which will be estimated by Clopper-Pearson exact method. The response rate difference between SURF-100 and each of the comparison treatment groups will be reported as well, with 95% CI of the difference estimated by the method of Newcombe with continuity correction. The difference in response rate between SURF-100 and other comparison treatment groups will be compared by Fisher's exact method.

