8. CLINICAL ASSESSMENTS/EXAMINATION PROCEDURES

Subject Completed Assessments:

UNC DEMS Questionnaire: The UNC DEMS will be completed by subjects at Visit 1 (Screening; Day -14 to Day 0) and only at Visit 2 (Day 0) if Visit 2 is >5 days following Visit 1. The UNC DEMS will also be completed by subjects at Visit 3 (Day 7) through Visit 7 (Day 98).

Dosing Diary with Drop Comfort Questionnaire: Subjects will be given a Dosing Diary with Drop Comfort Questionnaire to record study drug dose instillation dates and times for each dose, as well as to record their responses to the Drop Comfort Questionnaire every 7 days during the dosing period (Day 0 to Day 83).

Investigator Assessments:

Best-Corrected Visual Acuity (BCVA): BCVA will be performed in both eyes at Visit 1 (Screening; Day -14 to Day 0) and only at Visit 2 (Day 0) [prior to randomization] in both eyes if Visit 2 is >5 days following Visit 1. BCVA will also be performed in treated eyes at Visit 3 (Day 7) through Visit 7 (Day 98). Log of the minimum angle of resolution [logMAR] score using ETDRS [Early Treatment Diabetic Retinopathy Study] chart will be used to measure BCVA. Performing a pinhole test is allowed as long as its use remains consistent for the same subject throughout all study visits.

Biomicroscopy: Slit lamp biomicroscopy will be performed to observe the overall health of the eye, including the lid/lashes, conjunctiva, cornea, anterior chamber, iris, and lens. This will be performed in both eyes at Visit 1 (Screening; Day -14 to Day 0) and only at Visit 2 (Day 0) [prior to randomization] if Visit 2 is >5 days following Visit 1. Slit lamp biomicroscopy will also be performed in treated eyes at Visit 3 (Day 7) through Visit 7 (Day 98).

Ophthalmoscopy: An undilated ophthalmoscopy exam will be performed in both eyes at Visit 1 (Screening; Day -14 to Day 0) and in treated eyes at Visit 7 (Day 98).

Intraocular Pressure (IOP): IOP will be measured in both eyes at Visit 1 (Screening; Day -14 to Day 0) and only at Visit 2 (Day 0) [prior to randomization] if Visit 2 is >5 days following Visit 1. IOP will also be measured in treated eyes at Visit 3 (Day 7) through Visit 7 (Day 98).

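### A subject who leaves before Day 84 with an improved last UNC DEMS score counts as a Day 84 responder, and no analysis of the primary endpoint counts such leavers as failures

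*Combined protocol and SAP*

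**What the plan says.** Section 10.4 sets the approach: "an ITT analysis with the last-observation-carried-forward (LOCF) method will be conducted for the primary efficacy analysis". Section 11.1 repeats it ("For the ITT analysis, subjects with a missing UNC DEMS score at a visit will be imputed by the LOCF method") and concludes: "Therefore, there will be no missing data for ITT analysis". The population is everyone randomised; section 10.3 reads: "The Intent-to-Treat (ITT) population includes all randomized subjects".

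Section 10.5 deals with exit visits. For a subject who discontinues before Visit 6, "the data from the early discontinuation visit will be included in Visit 6/Day 84 assessment".

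The only rule that overrides the score is in sections 10.2 and 11.1: use of another dry-eye therapy at or before Visit 6 makes the subject a failure. Leaving the study, for whatever reason, is not a failure criterion.

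Section 10.3 also defines a per-protocol set of subjects "who have no significant protocol deviations during the study". Section 11.1 describes no analysis on that set, and the definition does not say how leavers are handled. The mixed models in section 11.2 cover TBUT and Schirmer only.

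**The concern.** The endpoint is response at Day 84, but an unrescued leaver is judged on the last score before leaving. Three features of this trial make that more than a formality.

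- The threshold is low, so a small early improvement is enough to qualify.
- The failure rule for other therapy depends on that therapy being recorded. The text describes recording of concomitant medication during the study, but not of treatment started after exit. A leaver who then switches therapy before Day 84 can remain a responder.
- Arms are small, so a few leavers can move a response rate by several points.

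Unequal dropout is plausible, though not shown. Section 6 reports ocular burning in 17% with cyclosporine and lists instillation-site irritation among reactions seen in 5-25% with lifitegrast. It states that adverse reactions to topical mycophenolic acid are not established. LOCF could therefore favour either side. With a single analysis, nobody could see how much of each arm's rate rests on leavers.

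**Working it through.** The documents give no dropout rate, assumed response rate or power calculation, so there is no stated figure to reproduce.

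**Inputs from the documents**
- Baseline UNC DEMS 5 to 9 (section 4.1).
- Responder threshold: a reduction of at least 10% (section 11.1).
- Post-baseline UNC DEMS visits before Day 84: Days 7, 30 and 60 (sections 2 and 8).
- 280-350 subjects in 7 balanced groups (section 2): 280/7 = 40 to 350/7 = 50 per arm.

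**Rule trace.** Take a subject who leaves before Visit 6 without other therapy and whose last score is at least 10% below baseline. If that score came from the exit visit, section 10.5 makes it the Visit 6 value. Otherwise LOCF carries it to Visit 6. Either way the responder definition is met and the override does not apply.

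**How little improvement is needed.** A one-point fall is 1/5 = 20.0%, 1/6 = 16.7%, 1/7 = 14.3%, 1/8 = 12.5% or 1/9 = 11.1% of baseline. All exceed 10%.

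**Age of a carried score at Day 84.** From Day 7: 84 - 7 = 77 days. From Day 30: 54 days. From Day 60: 24 days.

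**Effect within an arm.** Let d be the proportion leaving unrescued before Visit 6, and s the share of those with an improved last score. LOCF exceeds a leavers-as-failures analysis by d × s. For s from 0 to 1, the excess in points is:

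| assumed d | excess |
|---|---|
| 5% | 0-5 |
| 10% | 0-10 |
| 15% | 0-15 |
| 20% | 0-20 |

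**Effect on the difference between arms.** The shift is d1 × s1 - d2 × s2, which is zero when d and s are equal in both arms.
- Assumed d of 5-15% and s of 25-75%: the maximum is 0.15 × 0.75 - 0.05 × 0.25 = 0.1125 - 0.0125 = 0.10, so -10 to +10 points.
- Assumed d of 5-20% and s of 0-100%: the maximum is 0.20 × 1 - 0.05 × 0 = 0.20, so -20 to +20 points.

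**Illustration A** (assumed counts, 40 per arm, half of leavers improved, 24 and 19 completer responders throughout)

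| leavers | LOCF | difference | leavers as failures | difference |
|---|---|---|---|---|
| 6 v 2 | 27/40 v 20/40 | +17.5 | 24/40 v 19/40 | +12.5 |
| 4 v 4 | 26/40 v 21/40 | +12.5 | 24/40 v 19/40 | +12.5 |
| 2 v 6 | 25/40 v 22/40 | +7.5 | 24/40 v 19/40 | +12.5 |

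Holding the responder counts fixed isolates the LOCF contribution. It also means that the completer response rates change between rows.

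**Illustration B** (assumed, 50 per arm, completer response rates held near 70% and 45%, about 80% of leavers improved, two-sided Fisher's exact test)

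| leavers | LOCF | difference, p | leavers as failures | difference, p |
|---|---|---|---|---|
| 10 v 2 | 36/50 v 24/50 | 24, 0.024 | 28/50 v 22/50 | 12, 0.32 |
| 5 v 5 | 35/50 v 24/50 | 22, 0.041 | 31/50 v 20/50 | 22, 0.045 |
| 2 v 10 | 36/50 v 26/50 | 20, 0.063 | 34/50 v 18/50 | 32, 0.0025 |

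With unequal dropout, the rule for leavers can decide which side of 0.05 the result falls on. With equal dropout and an equal improved share, it barely matters.

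**The case against.** LOCF is prespecified consistently in two sections, so this is neither a contradiction nor a computing error. In a Phase 2 trial, one more table may look like a refinement. The plan already fails subjects who take other therapy, and leavers without an improved last score are non-responders under LOCF too. Only unrescued, improved leavers remain, and their number is unknown. Because there is an exit visit, many carried scores will be fresher than 77 days. The one-point threshold applies to completers as well.

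The strongest point concerns the remedy. Counting leavers as failures is also a single-imputation rule. It discards observed exit scores and reacts strongly to unequal dropout: in Illustration B its difference runs from 12 to 32 points when the imbalance is reversed, while LOCF runs from 24 to 20.

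Most of this stands, and it limits what can be claimed. No bias between arms has been demonstrated, and the added analysis is no more neutral than LOCF. It does not remove the gap. The two rules make opposite assumptions about improved leavers, and the plan reports only the favourable one. Showing both reveals how far the conclusion depends on that choice.

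**Conclusion.** The concern holds. Under sections 10.4, 10.5 and 11.1, an unrescued leaver with a last score at least 10% below baseline is a Day 84 responder. The available text, which ends within section 12.1, contains no analysis of the primary endpoint that counts such leavers as failures.

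The size cannot be fixed from the documents. On the assumed ranges above, an arm's rate is raised by 0 to 20 points. The difference between arms shifts by up to 10 points either way on the narrower assumptions and 20 on the wider ones, and by nothing if dropout and the improved share are equal. The direction is unknown. The primary result can still be computed, so this should be fixed but is not fatal.

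A smaller point of clarification: the statement that no data will be missing holds for dosed subjects only if a pre-dose score may be carried forward, which is not stated. The baseline definition in section 10.6 has no reference time for a randomised subject who was never dosed.

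**What to change.** In section 11.1, before unmasking:

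1. Add a prespecified analysis of the Day 84 response rate over all randomised subjects. Any subject who discontinues the study before Visit 6 is a non-responder, whatever the last or exit-visit score. Report it beside the LOCF result, which can remain primary.
2. State that the section 10.5 placement of exit-visit data at Visit 6 does not apply to this analysis.
3. State that subjects who stay in the study and miss only the Visit 6 score are not failed by this rule and keep LOCF.
4. For both analyses, state that a subject with no post-baseline score, including one never dosed, is a non-responder and stays in the denominator. Reword the sentence on missing data to match.

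The cost is a few sentences in 11.1, one exception to 10.5, one derived flag and one table. No new data are needed. The downside is that, in the added analysis, each arm's rate falls by at most its discontinuation rate and the arm with more dropout is penalised. That is why the two results should be read together.
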